5. STUDY POPULATION AND ELIGIBILITY CRITERIA

5.1 Population for Randomization

The population for randomization is adult SCD patients with the following Inclusion and Exclusion criteria.

The selection criteria below were designed to be inclusive and representative of the SCD population, including appropriate representation of women.

5.1.1. Inclusion Criteria

- 1) ≥ 18 years of age
- 2) SCD patients with the following genotypes:
 - a. Hgb SS, SC and SB+, SB- thalassemia

5.1.2. Exclusion Criteria

- 1) Patients with sickle cell trait
- 2) Patients with a treatment protocol that does not allow administration of opioids
- 3) Patients with an existing ED protocol that includes oral opioids only
- 4) Patients prescribed buprenorphine-containing medication in the outpatient setting
- 5) Patients prescribed methadone

5.2 Population for Enrollment

The population for enrollment is randomized patients with the following inclusion and exclusion criteria.

5.2.1. Enrollment Inclusion Criteria:

- 1) Patient is randomized
- 2) ED visit for VOE requiring parenteral opioid analgesia

5.2.2. Enrollment Exclusion Criteria

- 1) Patients presenting to the ED with other complications (e.g., acute chest pain, stroke, sepsis, priapism and other pulmonary complications) not clinically appropriate/stable for inclusion

6. TREATMENT INTERVENTIONS

6.1. Overview of Treatment Interventions

This will be a single-blinded two-arm randomized clinical trial comparing:

- Patient-specific analgesic protocol to treat VOE in adults with SCD
- Weight-based analgesic protocol to treat VOE in adults with SCD

There is currently no standard approach to managing VOE pain in the ED, resulting in wide variability in ED-based pain management. Patients will be randomized to either a patient-specific analgesic protocol or a weight-based analgesic protocol to treat VOE during an ED visit.

6.2. Blinding

The provider will be un-blinded to the analgesic protocol at the time of the patient visit to the ED.

Patients will be told what drug and dose they are receiving during their study ED visit. However, they will remain blinded to the analgesic protocol to which they are randomized. The research assistant performing the study assessments will also remain blinded to the randomized analgesic treatment protocol until all assessments have been completed.

6.3. Patient Safety and Concomitant Therapies

This study will evaluate and compare analgesic treatment protocols to treat VOE in adult patients with SCD during an ED visit.

7. RECRUITMENT AND SCREENING PROCEDURES

7.1. Common Recruitment/Screening Procedures

Patients meeting eligibility criteria for randomization population will be approached regarding participation in this study. The Site Investigators will train all research staff in screening and approaching patients for participation, consent, and data collection.

Patients will be recruited during an outpatient visit at hematology/SCD clinic, during an inpatient hospitalization, or at the end of an ED visit. Patients will consent for participation in the study during a subsequent ED visit for VOE, should one occur during the study

enrollment period. This procedure is very effective because patients can provide a more informed consent when not in severe pain. It would also not be feasible to enroll patients during an actual ED visit because the delay in analgesia associated with consulting the hematologist for the immediate development of the analgesic protocol and placement in the EMR. Community recruitment is also not feasible because we need a local hematologist to write the analgesic protocol and implement it in the hospital's EMR.

Inpatient Hospital Recruitment – The study staff at each site will round daily on the inpatient units to recruit subjects. Patients admitted to the hospital will be approached for possible participation only after obtaining permission to speak with the patient from a member of the clinical care team. If the patient is in too much pain, the study staff will return at a later date/time to discuss possible enrollment.

Hematology/SCD Clinic Recruitment – Study staff at each site will work closely with the clinic providers to determine the least intrusive manner to approach patients for participation and consent during routine clinic visits. All patients meeting study inclusion criteria will be approached for possible participation.

ED Recruitment – Study staff at each site will recruit those ED patients being discharged home who have not previously declined participation or already not been consented for this study. If the patient agrees to participate, they will sign the consent to participate in the study during a subsequent ED visit for VOE.

7.2 Estimated Enrollment Period

This study will randomize approximately 460 patients at approximately six U.S. study sites in order to enroll 230 subjects with an ED visit for VOE in the study population. The projected timeline for enrollment is approximately 24 months.

8. INITIAL STUDY EVALUATIONS AND RANDOMIZATION

A complete schedule of assessments throughout the study is provided in Appendix A.

8.1. Screening for Informed Consent and Patient Randomization

Potential trial patients believed to meet study selection criteria for the randomization population will be approached and willing patients will be consented for trial participation. After providing informed consent and signing the informed consent form (ICF), trial eligibility criteria will be formally confirmed. Patients will be randomized. Patients' characteristics will be collected at the time of randomization. After we have reached the target ED visit sample size in the study population, we will notify the patients remaining in the randomization population by phone, a subsequent clinic visit or by mail that the study enrollment has been completed and their randomized analgesic protocol will be removed from the EMR.

8.2. Randomization and Patient Analgesic Protocols

After patients have provided informed written consent, they will be randomized to either

the weight-based analgesic protocol or a patient-specific analgesic protocol that will be developed by their hematologist/sickle cell team. A 1:1 treatment allocation will be used with site as the stratification variable. A computer-generated permuted block randomization schedule with stratification by clinical site will be prepared by the DCC senior statistician with block size randomly chosen that will not be revealed to investigators. This scheme provides chronological balance during enrollment with respect to the number of patients allocated to each treatment arm, and thus balances the treatment groups with respect to possible changes in the mix of patients over time. For the sites, the randomization will be available through the password protected and customized web-based electronic data capture (EDC) system. The EDC will be maintained by the DCC data management team. Treatment plans can be updated as needed by the hematologist.

8.2.1 Patient-Specific Analgesic Protocol

If the patient is randomized to the patient-specific analgesic protocol, the outpatient SCD provider will develop a patient-specific analgesic protocol based upon chronic opioid therapy, if relevant, and past successful ED treatment. The procedure for developing patient-specific analgesic protocols is as follows: A member of the outpatient SCD provider team will review the patient's medical record to determine: 1) the patient's maximum home opioid dose, and 2) previous ED analgesic medication(s) and doses that have been effective and safe in the past.

Starting Dose determination:

Step 1: Calculate maximum home opioid dose and determine initial intravenous (IV) / subcutaneous (SC) ED VOE dose. IV and SC doses will be identical. Maximum home opioid dose is defined as the maximum dose of prescribed opioids typically taken by the patient at home in any 24-hour period. The maximum will be calculated by combining all long acting and short acting opioids taken within a 24-hour period and converting that medication to IV morphine sulfate equivalents (IVMSE). The SCD team member will use the maximum home opioid dose to generate a suggested starting dose of IV opioid for severe VOE pain in the ED as follows: preliminary calculation of IV dose for next ED visit (based on home opioid consumption) = 20% of patient's maximum 24-hour home opioid dose converted to IV morphine and IV hydromorphone.

Step 2: Reconcile with past ED doses.

The first choice of opioid (Morphine or hydromorphone) will be based on review of the patient's medical record for pertinent medical history and which drug has been used in the past with greater success. The preliminary calculations above will then be compared to doses of opioids that have been administered to the patient in the ED in the past. If the ED doses and the calculated preliminary doses are within 10% of each other, the preliminary dose will be finalized for that patient's suggested patient-specific analgesic protocol for use at the next ED visit for VOE. If the discrepancy is greater than 10%, the SCD team member will adjudicate this case with the Pain Management Protocols, Clinical Oversight and Implementation Committee to choose a safe dose in the following manner. Whichever of the two doses (preliminary calculations based on home consumption or prior ED doses) is lower will be chosen as the final suggested dose for use at the next ED visit. The lower dose was chosen because it is perceived to be safer. In addition, dose escalation is

permitted at the SCD provider's discretion. For example, if the highest prior ED dose is less than half of the preliminary calculated dose, the highest prior ED dose would be selected and could be increased by 25% for use in the patient-specific analgesic protocol. However, if the previously used ED dose is less than a weight-based dose, a weight-based dose will be used to avoid use of an unreasonably low dose. Per the NHLBI recommendations for the treatment of VOE, the dose frequency for IV pain medication administration will be set at 20-30 minutes unless the SCD provider feels this is not safe.

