8.2.2 Weight-Based Analgesic Protocol

The NHLBI recommendations will be used to develop the weight-based analgesic protocol; there are some similarities to the patient-specific analgesic protocol, namely dosing intervals and routes. The NHLBI recommendations include a starting dose be based on prior analgesic use. This can be difficult for a patient to accurately report at times. ED providers are typically not proficient in calculating and converting oral, or patch, opioid dosing to intravenous doses and are unlikely to do this on a widespread, national basis. Instead, we opted to make one adaptation to the expert panel recommendations for a "standard" VOE protocol; the initial dose will be weight-based. We chose weight-based because there is no current "standard" VOE protocol and weight-based opioid dosing is an acceptable alternative in other pain conditions, including cancer. As recommended by the NHLBI guidelines, the weight-based analgesic protocol will include re-assessment and re-dosing every 20-30 minutes, with one possible dose escalation of 25%. Table 1 provides an example of typical weight-based doses. A 5:1 conversion of morphine sulfate to hydromorphone (7.5 mg:1.5 mg morphine sulfate to hydromorphone) was used to calculate doses for both the weight and patient-specific doses.³⁰

Table 1. Weight-Based Doses for Morphine Sulfate and Hydromorphone

Weight range (kg)	Morphine dose (mg)
<50	4
50 – 69.9	6
70 – 89.9	8
≥ 90	10
Weight range (kg)	Hydromorphone dose (mg)
<60	1
60 – 89.9	1.5
≥ 90	2

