8.3 Odd Volume Doses for both analgesic protocols: One barrier to analgesic protocol implementation was the odd doses that resulted in the need to administer a volume of drug less than the amount in which it was supplied. This required “wasting” by the ED nurses and verification by a second nurse. We have consulted with a multidisciplinary team consisting of a pain expert, adult hematologist, and an emergency department physician to determine a strategy to select a final dose that will minimize the need for odd doses and wasting procedures (e.g. morphine 4.3 mg, or hydromorphone 1.3 mg). All doses of morphine can be ordered in increments of 2 mg and doses of hydromorphone can be ordered in increments of 0.5 mg. These doses remain consistent with the patient-specific and weight-based doses with rounding to a safe dose, and will significantly reduce the need to waste drug in most cases. We used this information when creating Table 1. Table 2 describes differences between analgesic protocols in agent, dose, route, monitoring, repeat doses and hydration. The primary difference between analgesic protocols is dose and the provision to increase weight-based doses if insufficient pain relief.

Table 2: Comparison of NHLBI Recommendations: Patient specific vs. Weight-based analgesic Protocol

	Patient-specific analgesic protocol	Weight-based SCD analgesic protocol
Agent	To be determined (TBD) by SCD provider after randomization for use at a future ED visit (morphine sulfate or hydromorphone)	To be determined (TBD) by SCD provider after randomization for use at a future ED visit (morphine sulfate or hydromorphone)
Dose	TBD a priori by SCD provider, based upon current outpatient opioid therapy, if applicable, and past doses required to treat VOE during past ED visits or hospitalizations.	TBD a priori by SCD provider. Initial dose = weight based hydromorphone 0.02 mg/kg morphine sulfate 0.1 mg/kg
Route	Intravenous (IV) unless unable; Sub-cutaneous when IV access is difficult.	Intravenous (IV) unless unable; Sub-cutaneous when IV access is difficult.
Monitoring	Per routine standard of care Q 30 minutes per research protocol / research assistant (sedation level, SpO ₂ , BP, HR, RR).	Per routine standard of care Q 30 minutes per research protocol / research assistant (sedation level, SpO ₂ , BP, HR, RR).

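### The weight-based floor in the patient-specific dosing rule tests only the prior ED dose, so the default suggested starting dose can fall below the weight-based dose

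*Protocol*

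**What the plan says.** Protocol section 8.2.1 builds the patient-specific starting dose in two steps.

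- **Step 1.** The home-based (preliminary) dose is 20% of the maximum 24-hour home opioid dose, in IV morphine equivalents. The provider bases the protocol on chronic opioid therapy only where relevant. The record review also looks for "previous ED analgesic medication(s) and doses that have been effective and safe in the past".
- **Step 2.** If the home-based dose and the prior ED dose are within 10% of each other, the home-based dose is finalized. If they differ by more, the case is adjudicated with the Pain Management Protocols, Clinical Oversight and Implementation Committee, and whichever of the two "is lower will be chosen as the final suggested dose for use at the next ED visit". The reason given is: "The lower dose was chosen because it is perceived to be safer". Escalation at the provider's discretion is allowed.
- **Floor.** The condition is "if the previously used ED dose is less than a weight-based dose, a weight-based dose will be used". The same sentence gives its purpose: "a weight-based dose will be used to avoid use of an unreasonably low dose".

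Section 8.2 adds: "Treatment plans can be updated as needed by the hematologist". Table 1 in section 8.2.2 gives the weight-based doses. SAP section 7.5 tabulates agreement between the assigned and administered initial dose and adds nothing to the rule. Neither document tests the home-based dose or the final dose against the weight-based dose.

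**The concern.** The floor exists to prevent an unreasonably low start, but it looks at only one of the two doses that can be low. A patient with low home opioid use whose prior ED dose was at or above weight-based gets the home-based dose, and nothing in the rule lifts it. The rule is also non-monotone: with weight and home use held fixed, a higher prior ED dose can produce a lower suggested start.

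Protocol section 4 names the starting dose as the main difference between the arms, and section 8.3 names dose together with the provision for increasing weight-based doses. The primary hypothesis is that the patient-specific arm is superior. For the affected patients, the written default suggests a start below what the comparator arm would give.

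**Working it through.** **Notation.** H = maximum 24-hour home dose (mg IVMSE). P = home-based dose. E = prior ED dose. W = weight-based dose. D = default suggested dose.

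**Inputs.**
- P = 0.20 × H for morphine (section 8.2.1). For hydromorphone, P = 0.20 × H / 5, from section 8.2.2: "A 5:1 conversion of morphine sulfate to hydromorphone".
- W from Table 1: morphine 4, 6, 8, 10 mg; hydromorphone 1, 1.5, 2 mg.
- Increments from section 8.3: "All doses of morphine can be ordered in increments of 2 mg and doses of hydromorphone can be ordered in increments of 0.5 mg".

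**Rule as written.** D = P if P and E are within 10%; otherwise D = min(P, E). Then, if E < W, D = W.

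**When D falls below W.** Suppose P < W ≤ E. Within 10%, D = P < W. Beyond 10%, D = min(P, E) = P < W. In both cases E ≥ W, so the floor is not triggered. Running the rule over 32,160 combinations (H from 0 to 200, E from 1 to 40 mg, W of 4, 6, 8 or 10 mg), with the floor applied to both branches, showed D < W in exactly these cases.

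**Morphine, 75 kg, W = 8, H = 20.** P = 0.20 × 20 = 4 mg.

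| E (mg) | Lower of P and E | E < 8? | D (mg) |
|---|---|---|---|
| 12 | 4 | no | 4 |
| 10 | 4 | no | 4 |
| 8 | 4 | no | 4 |
| 6 | 4 | yes | 8 |

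**Hydromorphone, 75 kg, W = 1.5, H = 25.** P = 0.20 × 25 / 5 = 1.0 mg. E = 2 or 1.5 gives D = 1.0; E = 0.5 triggers the floor and gives D = 1.5.

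All these doses lie on the section 8.3 increments, so rounding does not change them. E of 4 mg (morphine) or 1 mg (hydromorphone) equals P and so falls in the within-10% branch. These give 8 mg and 1.5 mg only if the floor sentence is assumed to reach that branch; otherwise they give 4 mg and 1 mg.

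**Within-10% case.** W = 8, E = 8, H = 37.5 gives P = 7.5. The difference is 0.5/8 = 6.25%, so 7.5 mg is finalized before rounding and no adjudication is required.

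**Home use at which the gap opens, given E ≥ W.** Section 8.3 does not state a rounding direction, so all three are shown.

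| Rounding | Morphine, W = 4/6/8/10 | Hydromorphone, W = 1/1.5/2 |
|---|---|---|
| None or down: H below W/0.20, or 5W/0.20 | 20/30/40/50 | 25/37.5/50 |
| Nearest (assumed): H below (W−1)/0.20, or 5(W−0.25)/0.20 | 15/25/35/45 | 18.75/31.25/43.75 |
| Up (assumed): H at or below (W−2)/0.20, or 5(W−0.5)/0.20 | 10/20/30/40 | 12.5/25/37.5 |

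The gap exists under every convention.

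**With the floor on the final dose**, D = max(D, W), and every 75 kg example above becomes 8 mg or 1.5 mg.

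**The case against.** The strongest reply is that the protocol does not leave this dose to a formula. Every below-weight example in the 75 kg cases differs by more than 10%, so each goes to the committee for a safe dose. The home-opioid input is qualified as applying where relevant, and low home users are the group for whom it may be least relevant. Escalation is discretionary, and the 25% figure is an example, not a cap. The hematologist can update the plan. Repeat doses may follow every 20–30 minutes, with no maximum set in the patient-specific arm. A clinician could also read the floor by its purpose and apply it to any selected dose.

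Most of this stands as mitigation. It does not remove the fault. The committee is given a rule, and the rule is to take the lower dose. The text does not say when home opioid use counts as relevant. Escalation and updating are permitted but not required, and the only escalation example concerns a low prior ED dose. Nothing requires at least the weight-based dose. If the authors meant the floor to cover the final dose, the sentence should say so.

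The safety reason for taking the lower dose does not explain the pattern either. The rule gives 8 mg to the patient with a 6 mg prior dose and 4 mg to the patient with a 10 mg prior dose. The comparator arm sets its initial dose by weight regardless of home use, so the protocol already accepts that dose for low home users.

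Three stronger inferences are not supported:
- *That patients will actually be under-dosed.* The rule yields a suggestion that several people can change.
- *That the record shows the weight-based dose was effective and safe for these patients.* The review seeks such doses, but the Step 2 comparison uses doses that were administered, and no general rule says which of several prior doses counts. The record shows only that a dose at or above weight-based was given before.
- *That the trial loses a stated amount of power.* The documents give no share of affected patients, so any figure would rest on an invented one.

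**Conclusion.** The point holds as a faulty default. On the literal wording, the suggested start is below the weight-based dose whenever the home-based dose is below it and the prior ED dose is at or above it. In the 75 kg morphine example it is half the comparator dose (4 mg against 8 mg), and the patient with the lower prior ED dose gets the higher start.

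That conclusion needs no assumption about rounding or about whether the floor reaches the within-10% branch; those affect only the exact cut-offs and the two examples flagged above. It does assume that the home-based dose is treated as relevant and that nobody overrides the default. How often that happens, and what it does to the treatment comparison, cannot be determined from the documents. The sentence should be corrected because its trigger misses cases its own stated purpose covers.

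**What to change.** Replace the floor sentence in section 8.2.1 with:

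*If the final selected dose (from either branch) is less than the weight-based dose, the weight-based dose will be used, unless the SCD provider or the committee judges this unsafe.*

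This also settles whether the floor covers the within-10% branch. It changes one sentence and leaves data collection and analysis as they are. The cost is a higher starting dose for some low home-opioid users, though the floor never lifts a dose above what the comparator arm would give the same patient. Prior ED doses carry no time window, so the override is needed for patients whose tolerance may have changed since.

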8.2.2 Weight-Based Analgesic Protocol

The NHLBI recommendations will be used to develop the weight-based analgesic protocol; there are some similarities to the patient-specific analgesic protocol, namely dosing intervals and routes. The NHLBI recommendations include a starting dose be based on prior analgesic use. This can be difficult for a patient to accurately report at times. ED providers are typically not proficient in calculating and converting oral, or patch, opioid dosing to intravenous doses and are unlikely to do this on a widespread, national basis. Instead, we opted to make one adaptation to the expert panel recommendations for a "standard" VOE protocol; the initial dose will be weight-based. We chose weight-based because there is no current "standard" VOE protocol and weight-based opioid dosing is an acceptable alternative in other pain conditions, including cancer. As recommended by the NHLBI guidelines, the weight-based analgesic protocol will include re-assessment and re-dosing every 20-30 minutes, with one possible dose escalation of 25%. Table 1 provides an example of typical weight-based doses. A 5:1 conversion of morphine sulfate to hydromorphone (7.5 mg:1.5 mg morphine sulfate to hydromorphone) was used to calculate doses for both the weight and patient-specific doses.³⁰

Table 1. Weight-Based Doses for Morphine Sulfate and Hydromorphone

Weight range (kg)	Morphine dose (mg)
<50	4
50 – 69.9	6
70 – 89.9	8
≥ 90	10
Weight range (kg)	Hydromorphone dose (mg)
<60	1
60 – 89.9	1.5
≥ 90	2

8.3 Odd Volume Doses for both analgesic protocols: One barrier to analgesic protocol implementation was the odd doses that resulted in the need to administer a volume of drug less than the amount in which it was supplied. This required “wasting” by the ED nurses and verification by a second nurse. We have consulted with a multidisciplinary team consisting of a pain expert, adult hematologist, and an emergency department physician to determine a strategy to select a final dose that will minimize the need for odd doses and wasting procedures (e.g. morphine 4.3 mg, or hydromorphone 1.3 mg). All doses of morphine can be ordered in increments of 2 mg and doses of hydromorphone can be ordered in increments of 0.5 mg. These doses remain consistent with the patient-specific and weight-based doses with rounding to a safe dose, and will significantly reduce the need to waste drug in most cases. We used this information when creating Table 1. Table 2 describes differences between analgesic protocols in agent, dose, route, monitoring, repeat doses and hydration. The primary difference between analgesic protocols is dose and the provision to increase weight-based doses if insufficient pain relief.

Table 2: Comparison of NHLBI Recommendations: Patient specific vs. Weight-based analgesic Protocol

	Patient-specific analgesic protocol	Weight-based SCD analgesic protocol
Agent	To be determined (TBD) by SCD provider after randomization for use at a future ED visit (morphine sulfate or hydromorphone)	To be determined (TBD) by SCD provider after randomization for use at a future ED visit (morphine sulfate or hydromorphone)
Dose	TBD a priori by SCD provider, based upon current outpatient opioid therapy, if applicable, and past doses required to treat VOE during past ED visits or hospitalizations.	TBD a priori by SCD provider. Initial dose = weight based hydromorphone 0.02 mg/kg morphine sulfate 0.1 mg/kg
Route	Intravenous (IV) unless unable; Sub-cutaneous when IV access is difficult.	Intravenous (IV) unless unable; Sub-cutaneous when IV access is difficult.
Monitoring	Per routine standard of care Q 30 minutes per research protocol / research assistant (sedation level, SpO ₂ , BP, HR, RR).	Per routine standard of care Q 30 minutes per research protocol / research assistant (sedation level, SpO ₂ , BP, HR, RR).
Repeat doses	TBD by SCD provider – Q 20-30 minutes as required to treat unrelieved pain. No maximum dose set.	Q 20-30 minutes for unrelieved pain. All additional doses, if required, may be provided at the same dose as the 1 st dose, or no more than a one time 25% increase above the original dose.
Intravenous hydration	Maintenance rate (unless dehydrated) when patients are unable to drink fluids adequately.	Maintenance rate (unless dehydrated) when patients are unable to drink fluids adequately.

Once the patient’s analgesic protocol has been developed (patient-specific or weight-based) by the hematologist/sickle cell team, the research team will be notified. The research team will ensure the analgesic protocol is uploaded to the electronic medical record (EMR) within one week of receipt. The analgesic protocol will be available in the EMR for future ED visits.

